11.4 Physical Examination

Clinically significant physical examination abnormalities will be recorded and summarized as medical history or AEs, as applicable.

11.5 Electrocardiogram

Descriptive statistics will be presented for data related to ECGs ([HR, RR, PR, QRS, QT, QTcB, and QTcF intervals). Observed values and change from baseline values will be presented for each post-baseline visit.

At nominal Day 1 and Week 24 visits, descriptive statistics for the observed values and change from pre-dose measurement in ECG parameters will be presented at pre-dose (observed values only) and 4 hours after treatment initiation. Frequency count and percentage will also be reported by treatment group for the following cardiac monitoring categories:

- HR < 40 bpm at the 4-hour post-dose timepoint
- HR < 50 bpm at the 4-hour post-dose timepoint

Additionally, an outlier analysis will be performed on all subjects with QTcF values > 500 msec or change from pre-dose measurement > 60 msec in the absence of pre-dose ECG abnormalities

that preclude accurate surface ECG assessment of ventricular repolarization (eg, bundle branch block); frequency and percentage of those subjects with QTcF values > 500 msec or change from pre-dose to 4-hour post-dose > 60 msec will be summarized for nominal Day 1 and Week 24 visit.

A listing of all ECG assessments will be provided. Overall interpretation with abnormal findings will be presented in the listing as well.

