S1P receptor modulators are associated with an expected, on target dose-dependent effect of reducing heart rate (HR) upon first dosing with HR recovery towards predose Baseline thereafter (Camm 2014). There have been no reported cases of symptomatic bradycardia on first dose, and rare first- or second-degree atrioventricular (AV) block found on ECG has been asymptomatic and transient (ie, spontaneous resolution) with etrasimod. A modest S1P₁-mediated HR reduction is maximal on the first day of dosing with etrasimod, which typically peaks approximately 3 hours postdose on Day 1 with recovery thereafter. In Study APD334-003, the mean transient HR decrease did not exceed 10 beats per minute (bpm) from Baseline on Day 1 up to 8 hours after dosing in all treatment groups, with the mean nadir of HR lowering for 2 mg etrasimod occurring 3 hours after dosing. This study includes an etrasimod 3 mg treatment group (refer to Section 3.3 for dose selection rationale). To attenuate the magnitude of HR reduction with the first etrasimod 3 mg dose, subjects assigned to etrasimod 3 mg will receive 2 mg once daily for 1 week, then escalate to 3 mg once daily; Phase 1 thorough QT (TQT) Study APD334-008 used a similar dosing paradigm. In Study APD334-008, the mean placebo-corrected change from baseline in HR was larger on Day 1 following 2 mg than on Day 8 and Day 13 when doses were escalated to 3 and 4 mg, respectively.

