17. History of malignancy of any organ system (other than localized squamous cell or basal cell carcinoma of the skin that have been excised or resolved), treated or untreated, within the past 5 years
18. Have any of the following conditions or receiving treatments that may affect cardiovascular function:
 - a. Myocardial infarction, unstable angina, stroke/transient ischemic attack, decompensated heart failure requiring hospitalization or Class III/IV heart failure within 8 weeks before Screening

- b. History or presence of second-degree or third-degree AV block, sick sinus syndrome, or periods of asystole for > 3 seconds without a functional pacemaker
 - c. Recurrent symptomatic bradycardia or recurrent cardiogenic syncope
 - d. Screening **OR** Baseline (Day 1) pre-randomization vital signs (taken in the sitting position) with an HR < 50 bpm, systolic blood pressure (BP) < 90 mm Hg, OR diastolic BP < 55 mm Hg. Vital signs may be repeated up to 3 times during a visit to confirm abnormal readings
 - e. Screening **OR** Baseline (Day 1) pre-randomization ECG with PR interval ≥ 200 ms or QT interval corrected using Fridericia's formula (QTcF) ≥ 450 ms in males or ≥ 470 ms in females
 - f. Start, stop, or change dosage of Class I-IV anti-arrhythmic drugs within 1 week of Screening
19. A history of or active diabetic retinopathy, uveitis, retinitis pigmentosum, or macular edema. Any recent intraocular surgery within 1 year of Screening
20. Active severe pulmonary disease (eg, chronic obstructive pulmonary disease or pulmonary fibrosis) or chronic pulmonary disease requiring intravenous corticosteroid treatment or hospitalization within 12 months before Screening or during the Screening Period
21. Have forced expiratory volume at 1 second (FEV₁) or forced vital capacity (FVC) < 70% of predicted values at Screening
22. Have any uncontrolled systemic disease(s) (eg, thyroid disorder, hypertension, diabetes). If the condition is considered controlled and the subject is on any medications (eg, thyroid medication or hormonal therapy) for treatment of diseases, the subject may be allowed to participate but must have been on a stable dose for at least 6 months prior to Screening and remain on a stable dose throughout the study.

Exclusionary criteria related to test or laboratory results (performed by central laboratory)

Note: A confirmed result means there have been 2 consecutive assessments showing a consistent abnormal, clinically relevant result.

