11.9.6. Electrocardiograms and Vital Signs

Individual ECG values will be listed by visit and summarized using descriptive statistics. Parameters to be provided for each ECG are HR and the following intervals: RR, PR, QRS, QT, QTc, and QTcF. Post-Baseline ECGs for each subject will be compared with the Baseline ECG. Any clinically significant change from Baseline may be recorded as an AE if deemed appropriate by the Investigator, or the Investigator in consultation with the Sponsor or delegate. Outlier analysis will be performed on all subjects with QTcF values > 500 ms or change from Baseline > 60 ms in the absence of Baseline ECG abnormalities that preclude accurate surface ECG assessment of ventricular repolarization (eg, bundle branch block).

Descriptive statistics for vital signs (BP, HR, respirations, and body temperature) will be presented by treatment group.

The change from Baseline for each of the vital signs and ECG parameters will be summarized. Incidence of abnormal vital signs parameters and outlier ECG results will be tabulated.

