2.2.1.4 Safety Endpoints

- Incidence and severity of adverse events (AEs) throughout the DB Treatment Period
- Incidence and severity of laboratory abnormalities and change from Baseline in laboratory values (to include hematology, serum chemistry, coagulation, and urinalysis) at Weeks 1 (Cohort 2 only), 2, 4, 8, 12, 16, 20, and 24
- Incidence of clinically significant vital sign abnormalities and changes from Baseline at 1-, 2-, 3-, and 4-hour post-dose on Day 1 as well as Weeks 1 (Cohort 2 only), 2, 4, 8, 12, 16, 20, and 24
- Electrocardiograms (ECG) at 4-hour post-dose on Day 1 as well as Weeks 12 and 24
- Holter Monitoring on Day 1 (Cohort 2 only) and Week 1 (Cohort 2 only)*
- Physical examination findings (abnormalities will be recorded and summarized as medical history or AEs, as applicable)

* The statistical analysis to be performed for these endpoints will be described in a separated SAP (refer to Section 1)

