4.4 Descriptive Statistics

All continuous variables will be summarized by presenting the number of subjects, mean, SD, median, minimum, and maximum. Categorical variables will be summarized using frequencies and percentages. Summary tables will be presented by treatment and visit, when applicable.

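### SAP 11.5 and Appendix 3 give no by-arm count of PR prolongation or ECG-read AV block, although the protocol uses both as safety criteria

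*SAP*

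**What the plan says.** **Protocol.** Section 1.2 reports that with etrasimod "rare first- or second-degree atrioventricular (AV) block found on ECG has been asymptomatic and transient". Exclusion 18e in Section 4.2 bars anyone with a "pre-randomization ECG with PR interval ≥ 200 ms". Section 4.3 applies the same PR limit before dosing at Week 24, for entry to the open-label extension. Table 7 (Section 10.5.7.4) sets the discharge criteria after first-dose monitoring; they include a heart rate criterion and absence of second-degree or higher AV block on ECG. Section 10.5.3 sends tracings to a central reader for final interpretation. Section 11.9.6 promises a tabulation of outlier ECG results but defines the outlier rule by QTcF alone. It also says: "Any clinically significant change from Baseline may be recorded as an AE if deemed appropriate by the Investigator".

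**SAP.** Section 11.5 begins "Descriptive statistics will be presented for data related to ECGs ([HR, RR, PR, QRS, QT, QTcB, and QTcF intervals", and Section 4.4 defines what that produces: "All continuous variables will be summarized by presenting the number of subjects, mean, SD, median, minimum, and maximum". For Day 1 and Week 24, Section 11.5 then says "Frequency count and percentage will also be reported by treatment group for the following cardiac monitoring categories". The categories are HR < 40 bpm and "HR < 50 bpm at the 4-hour post-dose timepoint", with the same time point for both. A separate outlier analysis covers QTcF > 500 msec or a change > 60 msec. Abnormal interpretations go to a listing. In Appendix 3 the only ECG outlier tables (14.3.6.2.1 and 14.3.6.2.2) are for QTcF. The ECG cardiac monitoring tables have titles that mention neither PR nor AV block.

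**Holter.** Protocol 11.9.5 names AV block among the arrhythmias that Holter is meant to detect. SAP 2.2.1.4 lists "Holter Monitoring on Day 1 (Cohort 2 only) and Week 1 (Cohort 2 only") as a double-blind safety endpoint and refers its analysis to a separate SAP.

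**The concern.** Safety of 2 mg and 3 mg is part of the primary objective. For a conduction effect, the useful quantity is how many subjects in each arm cross a limit or develop block. A mean change dilutes a few affected subjects among many unaffected ones. A maximum shows that at least one subject was affected, but not how many.

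The SAP gives threshold counts for other monitored risks: lung function, central foveal thickness, liver enzymes and lymphocyte grades. From Table 7 of the protocol it turns the heart rate criterion into a count but not the AV block criterion beside it. A finding that the protocol describes as asymptomatic and transient is also one that an investigator may reasonably not record as an AE.

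**Working it through.** The plan states no figure on this point, so there is nothing to reproduce. The check compares the documents and adds simple arithmetic on coverage.

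**1. Protocol criteria against SAP counts**

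| Protocol ECG or heart rate criterion | By-arm count in the SAP |
|---|---|
| Heart rate < 50 bpm (4.2, 4.3, Table 7) | Yes: 11.3 and 11.5 |
| QTcF limits (4.2, 4.3; outlier rule in 11.9.6) | Yes: outlier analysis in 11.5 |
| PR ≥ 200 ms (4.2, 4.3) | None: continuous summary only |
| Second-degree or higher AV block (4.2, 4.3, Table 7) | None: listing only |

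**2. Double-blind Holter coverage.** Inputs are the planned numbers in protocol 11.2 (Cohort 1: 24 on 2 mg, 12 on placebo; Cohort 2: 24 on 3 mg, 6 on 2 mg, 12 on placebo) and the Cohort 2 restriction in SAP 2.2.1.4.

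| Arm | Planned | With scheduled Holter | Without |
|---|---|---|---|
| 3 mg | 24 | 24 (100%) | 0 |
| 2 mg | 24 + 6 = 30 | 6 (6/30 = 20%) | 24 (80%) |
| Placebo | 12 + 12 = 24 | 12 (12/24 = 50%) | 12 (50%) |
| All | 78 | 42 | 36 (36/78 = 46%) |

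For the 36 Cohort 1 subjects, double-blind conduction data come from the 12-lead ECGs and AE reports.

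**3. What six subjects can show.** If no event is seen in n subjects, the one-sided 95% upper limit on the true rate is 1 − 0.05^(1/n).
- n = 6 (2 mg with double-blind Holter): 39.3%
- n = 30 (all planned 2 mg subjects, 12-lead ECG): 9.5%
- n = 24 (3 mg or placebo): 11.7%

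The two records differ in sensitivity, because Holter runs for 8 hours and an ECG is a snapshot. The figures compare numbers of subjects only.

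**4. What the continuous PR summary shows.** The values here are assumed; the documents give none. In an arm of 24, let PR rise by 40 ms in three subjects, taking each to 200 ms or more, and stay unchanged in 21.
- Mean change: (3 × 40)/24 = 5.0 ms
- SD: √[(3 × 35² + 21 × 5²)/23] = √(4200/23) = 13.5 ms
- Median 0, minimum 0, maximum 40 ms
- Incidence: 3/24 = 12.5%

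With one affected subject instead of three, the maximum is still 40 ms and the mean change is 40/24 = 1.7 ms. The incidence falls from 12.5% to 1/24 = 4.2%, and no line of the planned table reports it.

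**The case against.** A reader might infer that conduction harm would appear only as a mean PR change and a listing, and that no table could show how many subjects per arm developed it. The documents do not support that.

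- The PR summary includes the median, minimum and maximum, so an extreme value is visible.
- AV block recorded as an AE is counted by preferred term, severity, relationship and seriousness (SAP 11.1). It might also be flagged as an AE of special interest, but the term list is not supplied.
- Holter targets AV block, has its own SAP, and covers every planned 3 mg subject and the concurrent Cohort 2 placebo subjects in the double-blind period. Cohort 1 is scheduled for Holter at Weeks 24 and 25 in the extension.
- Second-degree block at 4 hours fails the discharge criteria, and failing again on re-monitoring leads to discontinuation. Discontinuation reasons are tabulated (SAP 7.1).

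A reader might also infer that the SAP dropped something the protocol had specified. It did not: protocol 11.9.6 limits the outlier rule to QTcF, so the gap starts there. The heart rate counts are monitoring categories, not part of the outlier analysis. With about 78 subjects, cases could also be counted by hand from the listing.

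These points narrow the concern but do not remove it. AE recording of an ECG change is left to the investigator. Disposition tables would not capture a block that resolves, and nothing says their reason categories would identify AV block. Double-blind Holter misses most 2 mg subjects and half of placebo. Whether the Holter SAP counts AV block cannot be confirmed. A hand count from a listing is not a pre-specified by-arm result.

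**Conclusion.** The gap is real and limited. The SAP has no categorical ECG summary by treatment group for PR prolongation or AV block. It matters most for Cohort 1 in the double-blind period: 24 of 30 planned 2 mg subjects and 12 of 24 on placebo have no scheduled Holter then, so their conduction findings reach a count only if recorded as AEs. The planned 3 mg arm has full double-blind Holter coverage, subject to what the separate SAP does with it.

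This rests on planned rather than actual numbers and on the text of SAP 11.5 and Appendix 3; table layouts are in a separate document that was not supplied. Nothing here implies that a conduction effect exists. The plan should be changed because the 12-lead ECG is the only conduction record scheduled in every randomized subject during the double-blind period, and it would yield no by-arm incidence.

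**What to change.** In SAP 11.5 and Appendix 3, add one table by treatment group, with counts and percentages at each scheduled ECG, at 4 hours post-dose on Day 1 and Week 24, and at any time post-baseline within each period, for:

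(a) PR ≥ 200 ms, among subjects whose centrally read pre-dose PR was < 200 ms (Day 1 pre-dose for the double-blind period, Week 24 pre-dose for the extension);

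(b) second-degree or higher AV block on the central ECG interpretation.

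The pre-dose condition in (a) is needed because eligibility may rest on the site reading while the final interpretation is central. Exclusion 18e alone therefore does not guarantee a central pre-dose value below 200 ms. The condition also covers any different entry limit under earlier Cohort 1 amendments. The QTcF outlier tables are already restricted by pre-dose value in the same way.

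This is a reporting change only. It uses a limit already in the protocol and alters no clinical rule. It complements the Holter analysis and does not replace it, because no 12-lead ECG is scheduled at the Week 1 step to 3 mg. The cost is SAP wording and one table from data already collected and centrally read. The counts per arm will be small and should be labelled descriptive.

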11.6 Pulmonary Function Test

Pulmonary function tests (PFTs) will be performed according to the Schedules of Assessments (refer to Appendix 1 and Appendix 2 in the protocol) and include forced expiratory volume at 1 second (FEV₁), forced vital capacity (FVC), and forced expiratory flow at 25 to 75% (FEF 25-75) measurements. Where locally available, diffusing capacity of the lungs for carbon monoxide (DLCO) measurements will also be performed.

The observed values and change from baseline values in each of the following PFT measurements will be summarized using descriptive statistics by visit:

- FEV₁ (L)
- % Predicted FEV₁
- FVC (L)
- % Predicted FVC
- FEV₁/FVC ratio
- % Predicted FEV₁/FVC ratio
- FEF 25-75 (L/sec)
- % Predicted FEF 25-75
- Total Lung Capacity (TLC; L)
- % Predicted TLC
- DLCO (mL/min/mmHg)
- % Predicted DLCO

Frequency count and percentage of subjects with markedly abnormal values will be reported by visit as well as at any time after baseline for each of the following predefined markedly abnormal criteria separately:

- % Predicted FEV₁ < 50%
- % Predicted FVC < 50%
- % Predicted FEV₁/FVC ratio < 50%

Incidence of subjects with potentially important PFT abnormal measurements will also be identified using the criteria below and summarized similarly:

- Decrease from DB baseline > 20% in FEV₁, i.e., percent change from DB baseline < -20%
- Decrease from DB baseline > 20% in FVC, i.e., percent change from DB baseline < -20%
- Decrease from DB baseline > 20% in DLCO, i.e., percent change from DB baseline < -20%

Shift tables from baseline to each scheduled post-baseline in Investigators' overall interpretation of the PFT (normal, abnormal NCS or abnormal CS) will be provided as well. Only subjects with a baseline result and a result at the specified post-baseline visit will be considered.

All PFT results and overall interpretation of PFTs will be listed and markedly, potentially important abnormal values will be flagged.

11.7 Ophthalmoscopy and Optical Coherence Tomography

A complete ophthalmoscopy and optical coherence tomography (OCT) assessment will be performed according to the Schedule of Assessments (refer to Appendix 1 and Appendix 2 in the protocol).

Frequency count and percentage of subjects in each result category of each ophthalmic exam test/part of the eye will be reported by visit. Observed values and change from baseline values in central foveal thickness (μm) and intraocular pressure (mmHg) will also be summarized using descriptive statistics by visit for each eye separately.

Frequency count and percentage of subjects with markedly increased central foveal thickness (as defined below) will also be reported by visit as well as at any time post-baseline:

- Increase from DB baseline in either eye > 40 μm in central foveal thickness

A listing of ophthalmoscopy (best corrected visual acuity- right eye, left eye, and combined) and all OCT assessments will be provided and markedly increased in central foveal thickness will be flagged. Additionally, separate listings for ophthalmic examination (eye pressure, slit lamp and dilated fundus) will also be provided.

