All safety data will be listed and summarized by treatment group. All treatment-emergent adverse events (TEAEs) will be coded using the Medical Dictionary for Regulatory Activities and tabulated by System Organ Class and Preferred Term. Incidence of AEs, SAEs, AEs leading to study drug discontinuation, and AESIs will be summarized and presented in descending order of frequency. Laboratory parameters will be summarized at each scheduled assessment timepoint using descriptive statistics. Associated laboratory parameters such as hepatic enzymes, renal function, and hematology values will be grouped and presented together. Individual subject values will be listed and values outside of the standard reference range will be noted. Shift tables and analyses of changes from Baseline will be produced. The change from Baseline for each of the vital signs and ECG parameters will be summarized. Incidence of abnormal vital signs parameters and outlier ECG results will be tabulated. Other safety assessments will also be analyzed in a descriptive way.

Efficacy Analysis:

The primary and secondary endpoints will be analyzed using the Full Analysis Set (FAS). The exploratory endpoints will be analyzed using the FAS and the Randomized Set. Other important statistical considerations, such as missing data imputation strategies, sensitivity analyses, and subgroup analyses will be described in the Statistical Analysis Plan.

The primary endpoint of percent change from Baseline to Week 24 in SALT I will be analyzed with a mixed-effects model repeated measures (MMRM) model. The MMRM model will include treatment group, visit, and interaction of treatment-by-visit as factors, and disease duration and Baseline SALT I score as covariates. An unstructured covariance matrix will be specified for the MMRM model. Least squares (LS) means at each visit and LS mean differences between treatment groups (each of the active arms versus placebo only) with p-values and corresponding 95% confidence intervals (CIs) will be reported. This method will also be applied to other score-based or continuous measures.

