10.5.7.7. Ophthalmic Symptom Monitoring

Based on reports of macular edema observed with the use of S1P receptor modulators fingolimod and siponimod, approved for relapsing multiple sclerosis ([GILENYA 2010](#), [MAYZENT 2019](#)), ophthalmic testing, including OCT, will be assessed in this study at Screening, Week 12, Week 24, Week 52, and ET if applicable ([Appendix 1](#) and [Appendix 2](#)).

Subjects experiencing unexpected ophthalmic symptoms, including blurred vision, decreased visual acuity, or other clinically significant ocular AEs, without a known/suspected etiology may need to have repeated ophthalmoscopy and OCT testing performed. If there is evidence of new onset macular edema considered related to study drug, then study drug should be interrupted as appropriate and the subject should be monitored closely with the appropriate diagnostic and clinical work-up.

Unscheduled ophthalmology visits in case of any visual complaint:

If, during the study, there are complaints of decreased vision or identification of worsening visual acuity (equal to or more than 2 lines on a standard eye chart using best corrected vision) then an unscheduled ophthalmic examination should be performed.

At an unscheduled ophthalmology visit, the eye examination will include

- Best corrected visual acuity measurement
- Ophthalmoscopy (may include contact lens biomicroscopy to examine the macula and optic disc)
- OCT for all subjects to investigate a suspected diagnosis of macular edema

Note: For both scheduled and unscheduled visits, in case of suspected macular edema based on the ophthalmoscopy or a relevant increase of central foveal thickness, then FA may be performed.

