Blurred vision	Intervention not indicated	Symptomatic; moderate decrease in visual acuity (best corrected visual acuity 20/40 and better or 3 lines or less decreased vision from known Baseline); limiting instrumental ADL	Symptomatic with marked decrease in visual acuity (best corrected visual acuity worse than 20/40 or more than 3 lines of decreased vision from known Baseline, up to 20/200); limiting self-care ADL	Best corrected visual acuity of 20/200 or worse in the affected eye	-
Definition: A disorder characterized by visual perception of unclear or fuzzy images.					

ADL, activities of daily life; CTCAE, Common Terminology Criteria for Adverse Events

Table 11: Example of CTCAE Terms and Grading for Laboratory Abnormalities and Pulmonary Functions Tests

CTCAE Term	Investigations				
	Grade 1	Grade 2	Grade 3	Grade 4	Grade 5
Alanine aminotransferase increased	>ULN - 3.0 × ULN if Baseline was normal; 1.5 - 3.0 × Baseline if Baseline was abnormal	>3.0 - 5.0 × ULN if Baseline was normal; >3.0 - 5.0 × Baseline if Baseline was abnormal	>5.0 - 20.0 × ULN if Baseline was normal; >5.0 - 20.0 × Baseline if Baseline was abnormal	>20.0 × ULN if Baseline was normal; >20.0 × Baseline if Baseline was abnormal	-

Definition: A finding based on laboratory test results that indicate an increase in the level of alanine aminotransferase (ALT or SGPT) in the blood specimen. Navigational Note: Also consider Hepatobiliary disorders: Hepatic failure
					
Aspartate aminotransferase increased	>ULN - 3.0 × ULN if Baseline was normal; 1.5 - 3.0 × Baseline if Baseline was abnormal	>3.0 - 5.0 × ULN if Baseline was normal; >3.0 - 5.0 × Baseline if Baseline was abnormal	>5.0 - 20.0 × ULN if Baseline was normal; >5.0 - 20.0 × Baseline if Baseline was abnormal	>20.0 × ULN if Baseline was normal; >20.0 × Baseline if Baseline was abnormal	-

Definition: A finding based on laboratory test results that indicate an increase in the level of aspartate aminotransferase (AST or SGOT) in a blood specimen. Navigational Note: Also consider Hepatobiliary disorders: Hepatic failure
					
Forced expiratory volume decreased	FEV ₁ (% (percentages of observed FEV ₁ and FVC related to their respective predicted values) 99 - 70% predicted	FEV ₁ 60% - 69%	50% - 59%	≤ 49%	-

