Table 14.3.7.1.1	Summary of Value and Change from Baseline in Pulmonary Function Tests - Double-Blind Treatment Period (Safety Set)
Table 14.3.7.2.1	Incidence of Markedly Abnormal and/or Potentially Important Pulmonary Function Test Values by Visit - Double-Blind Treatment Period (Safety Set)
Table 14.3.7.3.1	Shift from Baseline in Overall Interpretation of Pulmonary Function Tests - Double-Blind Treatment Period (Safety Set)
Table 14.3.8.1.1	Summary of Value and Change from Baseline in Central Foveal Thickness and Intraocular Pressure - Double-Blind Treatment Period (Safety Set)
Table 14.3.8.2.1	Incidence of Markedly Increased from Double-Blind Baseline in Central Foveal Thickness by Visit – Double-Blind Treatment Period (Safety Set)
Table 14.3.8.3.1	Summary of Ophthalmic Exam - Double-Blind Treatment Period (Safety Set)

Listing Number	Listing Title
Listing 16.2.11.1	Pulmonary Function Tests (Safety Set)
Listing 16.2.11.2	Overall Interpretation of Pulmonary Function Tests (Safety Set)
Listing 16.2.12.1	Ophthalmoscopy – Best Corrected Visual Acuity (Safety Set)
Listing 16.2.12.2.1	Optical Coherence Tomography – Central Foveal Thickness Measurement (μm) (Safety Set)
Listing 16.2.12.2.2	Optical Coherence Tomography – Other Notable Findings/Other Exams Performed (Safety Set)
Listing 16.2.12.3.1	Ophthalmic Exam – Eye Pressure Exam (mmHg) (Safety Set)
Listing 16.2.12.3.2	Ophthalmic Exam – Slit Lamp Exam (Safety Set)
Listing 16.2.12.3.3	Ophthalmic Exam – Dilated Fundus Exam (Safety Set)

Final Analysis

Table Number	Table Title
Table 14.1.1.0	Study Information
Table 14.1.1.1.4	Subject Disposition - Open-Label Extension Period (Open-Label Extension Safety Set)
Table 14.1.1.1.5	Subject Disposition – Open-Label Extension Period (Open-Label Extension Full Analysis Set)
Table 14.1.1.1.6	Subject Disposition – Full Study (Randomized Set)
Table 14.1.1.1.7	Subject Disposition – Full Study (Full Analysis Set)
Table 14.1.1.2.2	Analysis Sets – Open-Label Extension Period (Open-Label Extension Safety Set)
Table 14.1.2.4	Demographic and Baseline Characteristics - Open-Label Extension Period (Open-Label Extension Safety Set)
Table 14.1.2.5	Demographic and Baseline Characteristics - Open-Label Extension Period (Open-Label Extension Full Analysis Set)
Table 14.1.3.1.2	Important Protocol Deviations – Open-Label Extension Period (Open-Label Extension Safety Set)
Table 14.1.3.1.3	Important Protocol Deviations – Full Study (Randomized Set)

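### Best-corrected visual acuity is only listed, so no by-arm table shows how many subjects lost acuity; a lesser gap is that intermediate lung-function declines are not counted

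*SAP*

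**What the plan says.** **Eyes.** Protocol 10.5.6 includes best-corrected acuity in the Screening eye examination and in every scheduled one after it. Protocol 10.5.7.7 places these at Screening, Weeks 12, 24 and 52, and early termination, and gives macular oedema seen with other drugs of the class as the reason. The same section orders an unscheduled examination for "worsening visual acuity (equal to or more than 2 lines on a standard eye chart using best corrected vision". Protocol Table 10 grades blurred vision partly by acuity and lines lost.

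In the Safety Analysis part of the protocol synopsis, safety data are to be summarised by arm as well as listed, and "Other safety assessments will also be analyzed in a descriptive way". SAP 11.7 says of acuity only this: "A listing of ophthalmoscopy (best corrected visual acuity- right eye, left eye, and combined) and all OCT assessments will be provided". Appendix 3 matches, with a listing titled "Best Corrected Visual Acuity (Safety Set") and no acuity table for either study period.

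**Lungs.** Protocol 4.2 excludes anyone with low FEV1 "or forced vital capacity (FVC) < 70% of predicted values at Screening". Protocol Table 11 grades "Forced expiratory volume decreased" as Grade 2 at 60-69% of predicted, Grade 3 at 50-59% and Grade 4 at 49% or less. It grades vital capacity as Grade 2 below 75% down to 50%, and Grade 3 below 50%. SAP 11.6 plans the following: "Frequency count and percentage of subjects with markedly abnormal values will be reported by visit as well as at any time after baseline". The cut is 50% of predicted for FEV1, FVC and their ratio. It also counts falls of more than 20% from double-blind baseline in FEV1, FVC and DLCO.

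**The concern.** Safety in the double-blind period is part of the primary objective, and eye and lung testing is there because of known effects of the drug class. A listing lets a reader look up individuals. It does not say how many subjects were measured in an arm, how many worsened, or how that compares with placebo. For acuity that comparison is left to whoever reads the listing, with no definition of a loss fixed beforehand.

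The SAP handles comparable measurements differently. It counts lymphocytes by Grades 1 to 4, liver enzymes at several multiples of the upper limit, heart rate below 50 bpm, and foveal thickness rises above 40 µm. No reason is given for treating acuity otherwise.

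For lungs the issue is narrower. The counting rules leave a band of intermediate decline that Table 11 would grade but no tally picks up.

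**Working it through.** The plan states no figure on this point, so there is none to reproduce. The eye part is a comparison of text; the lung part is threshold arithmetic.

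**Eyes**

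1. Collected: acuity for each eye, at baseline and at scheduled visits (Protocol 10.5.6, 10.5.7.7, Appendices 1 and 2).
2. Promised: a descriptive summary by arm (protocol synopsis, Safety Analysis).
3. Planned eye tables (SAP Appendix 3): the 14.3.8.1 series covers foveal thickness and intraocular pressure, 14.3.8.2 covers marked rises in foveal thickness, and 14.3.8.3 is titled Ophthalmic Exam. Acuity is not named in any of them.
4. Could 14.3.8.3 include acuity? SAP 11.7 says: "Frequency count and percentage of subjects in each result category of each ophthalmic exam test/part of the eye will be reported by visit". Its closing sentence, however, describes the ophthalmic examination as pressure, slit lamp and fundus. Appendix 3 numbers those listings 16.2.12.3.1 to 16.2.12.3.3, apart from acuity at 16.2.12.1. Even if acuity were included, categories by visit would not give lines lost from baseline.
5. Declared as a change? SAP Table 4 has four entries (OLE baseline, FAS, Per Protocol Set, OLE FAS). None concerns eyes.
6. Scale: planned arms are 24 on 3 mg, 24 + 6 = 30 on 2 mg and 12 + 12 = 24 on placebo, 78 in all. One affected subject is 1/24 = 4.2% or 1/30 = 3.3% of an arm. The expected number of losses cannot be derived.

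**Lungs**

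Let B be baseline and F follow-up, both as % of predicted. Assume the predicted value is constant, so that the percentage fall in litres equals the percentage fall in % predicted. SAP 11.6 counts a subject if F < 50 or (B − F)/B > 20%. The lowest value the 20% rule leaves uncounted is 0.8 × B.

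- From the entry limit: 0.8 × 70 = 56. Going from 70 to 50 is already a fall of 20/70 = 28.6%. For eligible entrants, then, anyone below 50% is also caught by the 20% rule, and that rule decides who is counted.
- FEV1 Grade 3 (below 60) is reachable uncounted from B = 70 to just under 60/0.8 = 75.
- FEV1 Grade 2 (below 70) is reachable uncounted from B = 70 to just under 70/0.8 = 87.5.
- FVC Grade 2 (below 75) is newly reachable uncounted from B = 75 to just under 75/0.8 = 93.75. Entrants with FVC of 70 to below 75 are already Grade 2.
- FEV1 Grade 4 and FVC Grade 3 cannot be reached uncounted.

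| Measure | B to F | Fall | Table 11 | Counted? |
|---|---|---|---|---|
| FEV1 | 72 to 58 | 14/72 = 19.4% | Grade 3 | No |
| FEV1 | 80 to 65 | 15/80 = 18.75% | Grade 2 | No |
| FVC | 90 to 74 | 16/90 = 17.8% | Grade 2 | No |

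**The case against.** **Lungs.** A reader might infer that lung losses are never compared by arm. The documents do not support that.

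- SAP 4.4, 11 and 11.6 give observed values and changes in % predicted FEV1 and FVC by arm and visit, including the minimum, so a reader can see whether anyone in an arm fell below 70% or 60%.
- There are also two sets of counts and a shift table of the Investigator's interpretation.
- The 50% cut is Table 11 Grade 3 for FVC and in effect Grade 4 for FEV1.
- The 70% limit is a Screening exclusion, not an on-study threshold. Protocol 10.5.7.6 sets no numeric trigger, and Table 11 is headed as an example.
- A worst-grade table without a baseline condition would mislead, because entrants with FVC of 70 to below 75% would count as Grade 2 without any decline.

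All of this stands and confines the lung point to a missing count. A minimum shows one worst value, not how many subjects declined, and one subject in 24 falling 16 points moves the arm mean by only 16/24 = 0.7 point.

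**Eyes.** A reader might likewise infer that the macular oedema risk goes uncompared. It does not: foveal thickness, its marked rises and the examination findings are tabulated, and reported visual events appear in the adverse-event severity table. The 2-line figure prompts an examination and is not an analysis threshold. Acuity is not among the named safety endpoints (Protocol 11.9.1, SAP 2.2.1.4). Listings are sorted by arm. Table layouts sit in a separate document not available here.

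These points limit the severity but do not close the gap. Foveal thickness is anatomy, not vision. Under Protocol Appendix 5 a test result is graded only if the Investigator considers it an adverse event, and the 2-line rule does not itself create one. A sorted listing is not a summary, and the separate listing numbers make it unlikely that an acuity table is hidden under another title.

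**Conclusion.** The vision point holds. Acuity is collected at baseline and at every scheduled eye visit, the protocol says safety data will be summarised by arm, and the SAP lists acuity without declaring a change. As planned, no table gives the number of subjects per arm who lost acuity. This rests on the SAP text and output titles, since the table layouts were not available. The number of subjects affected is unknown, and in arms of 24 to 30 the result would be descriptive only.

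The lung point is secondary. By-arm comparison exists; what is missing is a count of intermediate declines, which can occur uncounted from FEV1 baselines of 70% to just under 87.5% of predicted and FVC baselines of 75% to just under 93.75%. Those bounds assume a constant predicted value. The matter is a cheap improvement worth making. It is not a flaw that undermines the safety analysis.

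**What to change.** **Main change.** In SAP 11.7 and Appendix 3, add a table by treatment group, by visit and at any time post-baseline, of subjects with a loss of 2 or more lines, and of more than 3 lines, in best-corrected acuity from double-blind baseline in either eye. Use the number of subjects measured as denominator. State the rule for converting Snellen values to lines, because Protocol 10.5.6 asks only for a standard chart (naming Snellen at Screening) and gives no conversion. Let the any-time row use all post-baseline measurements: SAP 4.3 keeps an unscheduled value only where the scheduled one is missing, and a visual complaint leads to an unscheduled examination.

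**Optional.** In SAP 11.6, add a shift table from baseline to worst post-baseline FEV1 and FVC by Table 11 category, counting only subjects whose category worsens. Keep the existing criteria.

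**Cost.** SAP wording, the conversion rule, and one or two extra tables from data already collected. No procedure or clinical rule changes. The less extreme categories will include some test-to-test variation, which the placebo column shows.
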